- 3) To compare the result between group 1 and group 2,so as to find out the possible benefits in the precise therapy group(group 1);
- 4) To promote the appliance of 3-D imaging techniques for patients with CTEPH, and establish a standard precise PEA strategy guided by enhanced CT scanning and pulmonary angiography,in order to further improve the surgical result for patients with CTEPH,especially for patients with peripheral changes.

3 Design and Method

1) General design

This is a randomized single-blinded controlled study, 72 cases of patients are expected to be enrolled into this study, and randomized into 2 groups. The endpoint of these 2 groups will be compared to determine the efficiency of the appliance of 3-D imaging techniques for PEA procedures.

2) Clinical data collection process:

Pre-operative period: From admission to the moment before surgeries. Basic clinical information including the patients' age, gender, symptoms, clinical diagnosis, WHO classes, disease history et al. Blood test such as the thrombus forming tendency test, blood coagulation function test, coagulation factor activity test and N-terminal B-type natriuretic peptide (NT-proBNP) et al were collected. Other examinations included CT scanning, MRI, CPET, RHC and pulmonary angiography, pulmonary nuclide perfusion imaging, respiratory function test and UCG et al. The major parameters of these examinations are collected.

[figure not shown]
Operation period: The RHC result immediately before and after PEA surgeries are documented, the anesthesia record and CPB record, surgical specimen pathological record, intra-operative cerebral oxygen saturation data will be collected;

Post-operative period before discharge: Pulmonary nuclide perfusion imaging, CT scanning and UCG should be done in this period.

Follow-up period: A routine 3-, 6-, 12-, 24 months follow-up will be done, the follow-up contents include the measuring of NT-pro BNP, UCG, CPET, CT scanning, RHC, pulmonary angiography, pulmonary perfusion imaging, MRI and RHC. Among which the CPET, MRI, RHC and pulmonary angiography should be done after 6 months after surgeries. All the redo examinations could be done in any follow-up period, but at least 1 time of these examinations should be done in the whole follow-up period, and the follow-up time should be recorded.

[figure not shown]
3) CT Imaging assessment:

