An example of precise therapy process.A,3-D CT constructed images,which can provide the detailed information of each pulmonary segmental shape and their distribution;B,enhanced CT imaging of pulmonary segment,to assess the occluded severity of each pulmonary segment;C:Diagrammatic sketch of pulmonary artery embolism's location,red marked font refer to pulmonary segments with occupying changes;as shown in the picture,the RA4,RA2,RA5 is completely occluded,other affected segment is partially occluded.D.Surgical specimen;the occupying lesions in each pulmonary segment is stripped according to the embolism location identified by high-resolution CT scanning(seen in picture C);E,clearly opened pulmonary segment entrance after precise stripping therapy.

Arm information:All the patients included into this study met the requirements above and randomized into 2 groups:

group 1:precise PEA therapy with the guide of 3-D imaging techniques;

group 2:traditional PEA therapy solely by surgical probe and traditional CT scanning/pulmonary angiography method.

100 cases of randomized group were generated,which consisted of 50 cases of group 1 and 50 cases of group 2, and 100 cases of randomized number was generated paralleled with the randomized group.According to the date of admission of each patients,they are included into the randomized group one by one,any patient met the criteria of the **not eligible** described above will be excluded from this experiment, and all the patients consent to participate in this study will not know their specific group, the chief surgeon can only know the random grouping situation after the patients been admitted into hospital.

5 Outcome measures and time frame

The primary endpoint for assessment of the efficacy was the peri-operative hemodynamic improvement, peri-operative mortality, major complications after surgery, and deaths in the follow-up period.

Secondary endpoint were the measuring values of NT-pro BNP, parameters of MRI, UCG and CPET in the follow-up period, the CT scoring changes from baseline to follow-up period, and WHO function classes in the follow-up period, as well as disease directly associated cost (average cost) in the follow-up period.

6 Statistical Analysis Plan

This is a prospective randomized single-blinded controlled study, the major endpoint is the hemodynamic improvement after the surgeries.

1) Sample Size:

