Sample size estimation was based on a hypothesis that the mean PAP of patients of PTG can be decreased by 8 mmHg more than that of the traditional group. Given the standard deviation of 12 mmHg was expected in the measurement of mean PAP, with a power of 80% and a significance statistically level of 5% on both side, a sample size of 36 of the PTG group was required.

2) Statistical Analysis:

The analysis was based on the principle of “Intention to Treat” (ITT). All randomized patients (regardless of whether they violate the protocol) will be included in the final analysis.

Continuous variables are presented as mean \pm standard deviation, unless otherwise specified. Significant differences were determined with the Mann-Whitney test or independent t-test according to the their distribution, Wilcoxon matched pairs signed rank test or paired t-test for the paired variables. Categorical variables were compared between the 2 groups using the chi-square test or Fisher exact test. Kaplan-Meier method was used to estimate survival, log-rank test was used to evaluate the survival difference between different groups.

The pulmonary occluded severity will be scored using CT scanning and pulmonary angiography for each patients, the scoring result will be compared with the hemodynamic result to investigate their possible correlations using Spearman Correlation Analysis.

All the statistical analysis were performed using SPSS version 22.0. P value less than 0.05 was considered statistically significant.

7 Quality Control

1) Data accuracy:

All the participants in this study are responsible for the data collection process, all the original medical document should be pictured or scanned as the evidence of recorded data; for parameters with possible subjective error, the original imaging or assessment profile should be saved, the parameters estimated by

2) Group coordination

Fuwai hospital was the largest cardiac surgery center in China and also one of the largest center in the world. Up to now, we had established a coordination team of CTEPH in our center, which consist of cardiac surgery department, pulmonary disease center, radiology department, intensive-care unit and ultra-sonic department, nuclear medicine department in our center.

All the imaging data had been evaluated by at least 2 professional staffs in that field, and the CT constructed imaging, pulmonary angiography imaging had been saved for re-assessment in case of possible subjective bias.

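### Improvement, not an error: mean PAP is compared between arms only by unadjusted tests, although the right-heart catheter value taken immediately before surgery is recorded and could be used as a covariate

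*Combined protocol and SAP*

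**What the plan says.** The opening of section 6 states that "the major endpoint is the hemodynamic improvement after the surgeries". Section 6, 1) Sample Size rests on the hypothesis that "the mean PAP of patients of PTG can be decreased by 8 mmHg more than that of the traditional group". On variability it says "Given the standard deviation of 12 mmHg was expected in the measurement of mean PAP". It sets 80% power and a two-sided 5% level, and the paragraph ends by stating that "a sample size of 36 of the PTG group was required".

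For continuous outcomes, section 6, 2) Statistical Analysis says "Significant differences were determined with the Mann-Whitney test or independent t-test according to the their distribution". For values measured twice in the same patient, the section has a separate rule: "Wilcoxon matched pairs signed rank test or paired t-test for the paired variables". This second pair of tests works within patients and does not compare the arms. The other methods listed are chi-square or Fisher tests, Kaplan-Meier with log-rank, and Spearman correlation between imaging score and hemodynamics. None adjusts for a baseline value.

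In section 3, under the operation period: "The RHC result immediately before and after PEA surgeries are documented". A pre-operative and a post-operative mean PAP should therefore exist for most patients.

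The plan does not say whether the between-arm test is applied to the change or to the post-operative value, nor which of these has the SD of 12 mmHg. The references to a greater decrease and to improvement favour change; the SD wording could mean a single measurement.

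**The concern.** Pre-operative mean PAP is likely to be among the best predictors of post-operative mean PAP. The planned between-arm tests either ignore it (post-operative value) or use it with a slope fixed at 1 (change). ANCOVA estimates the slope from the data.

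What is at stake is precision. The trial is small, with 72 patients planned, and is sized at 80% power. If the correlation is moderate, adjustment narrows the confidence interval without adding a patient, visit or measurement. ANCOVA also gives the same arm effect whether the outcome is written as the post-operative value or as the change, so it settles a choice that the plan leaves open.

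**Working it through.** **Inputs from the documents (section 6, 1):** difference 8 mmHg, SD 12 mmHg, two-sided 5%, power 80%, 36 in the PTG arm. Section 3 gives 72 in two groups, so 36 per arm.

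**Assumed, because the documents do not give them:** the pre-post correlation rho, the ratio of post- to pre-operative SD, and the shape of the distributions.

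**1. The plan's own figure.** n per arm = 2 × (1.960 + 0.842)² × 12² / 8² = 35.3, so 36. Exact power of the t-test at 36 per arm (noncentral t, 70 df, noncentrality 8 / (12 × √(2/36)) = 2.83) is 79.7%. The stated size is reproduced.

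**2. Formulas.** With equal pre- and post-operative SD s:
- variance of the post-operative value: s²
- variance of the change: 2s²(1 − rho)
- ANCOVA residual variance: s²(1 − rho²)

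ANCOVA variance is therefore (1 + rho)/2 times that of a change test and (1 − rho²) times that of a post-value test. Neither ratio exceeds 1. ANCOVA has 69 df instead of 70.

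**3. If 12 mmHg is the SD of change.** ANCOVA residual SD = 12 × √((1 + rho)/2). Equivalent n per arm = 36 × 2/(1 + rho).

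| rho | t-test on change | ANCOVA SD | ANCOVA power | 95% CI half-width (5.64 unadjusted) | equivalent n per arm |
|---|---|---|---|---|---|
| 0.3 | 80% | 9.67 | 93% | 4.55 | 55 |
| 0.5 | 80% | 10.39 | 90% | 4.89 | 48 |
| 0.7 | 80% | 11.06 | 86% | 5.20 | 42 |
| 0.8 | 80% | 11.38 | 84% | 5.35 | 40 |

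**4. If 12 mmHg is the SD of one measurement.** ANCOVA residual SD = 12 × √(1 − rho²); SD of change = 12 × √(2(1 − rho)).

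| rho | t-test on post value | t-test on change | ANCOVA |
|---|---|---|---|
| 0 | 80% | not tabulated | 80% |
| 0.3 | 80% | 65% | 83% |
| 0.5 | 80% | 80% | 90% |
| 0.7 | 80% | 95% | 97% |

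At rho 0.3 the gain is 3.5 points over a post-value test (79.7% to 83.2%) and about 18 points over a change test (65.5% to 83.2%). Both comparisons are needed, because the plan does not say which is tested.

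**5. Unequal SDs, SD of change 12.** At rho 0.3/0.5/0.7/0.8, ANCOVA power is 98/96/94/94% if the post-operative SD is 0.8 of the pre-operative SD, and 88/84/80/80% if it is 1.25 of it. In the last setting the pre-post slope is 0.8 × 1.25 = 1, so ANCOVA and the change test coincide.

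**6. Non-normal data (simulation, 36 per arm, SD of change 12, rho 0.5).**

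| Distribution | Mann-Whitney on change | ANCOVA | rank ANCOVA |
|---|---|---|---|
| normal | 78% | 90% | 87% |
| mild skew (lognormal, log-SD 0.3) | 82% | 90% | 92% |
| strong skew (lognormal, log-SD 0.8) | 98% | 90% | >99% |
| t with 3 df | 96% | 91% | 98% |

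With t(3) tails and rho 0.8 to 0.9, ordinary ANCOVA has about 86%, against about 95% for the planned t-test/Mann-Whitney rule on change. The plan gives no switching criterion, so Shapiro-Wilk p < 0.05 was assumed for that rule.

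**The case against.** The strongest reply is that nothing is wrong. The tests are valid under randomisation, the sample size matches them, and every gain depends on a correlation, an SD ratio and a distribution that the documents do not give. All of that stands, and it is why this is an optional improvement.

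A second reply is that a test on change already uses the baseline. It does, with the slope fixed at 1. ANCOVA gains nothing when the true slope is near 1, and nothing over a post-value test when rho is near 0.

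A third is that mean PAP may be skewed or heavy-tailed, where the planned Mann-Whitney option does well. This also stands. A rank-based ANCOVA recovers the loss at moderate rho but not always at very high rho. With t(3) tails and rho 0.9, a rule that switches to rank ANCOVA on a normality test had 93% against 96% under one way of generating the tails, and about 87% against 95% under another.

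A fourth concerns the covariate. Section 4 lets the chief surgeon learn the allocation after admission, so the RHC immediately before surgery may follow that knowledge. It still precedes the operation and patients are blinded, so it is a reasonable covariate. The RHC from the pre-operative work-up is an alternative.

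A reader might infer that the trial is underpowered or that 36 per arm is wrong, for instance from the 65% in step 4. The documents do not support that. The figure needs a test on change, 12 mmHg as the SD of one measurement, and rho 0.3, and the plan commits to none of these.

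**Conclusion.** The point holds as an improvement. The plan compares mean PAP between arms without adjustment while recording the value to adjust for, and its stated power of about 80% is correct for the planned tests if 12 mmHg is the SD of the quantity tested.

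Under approximate normality and equal SDs, ANCOVA adds about 4 to 13 points of power over a test on change when 12 mmHg is the SD of change (rho 0.8 down to 0.3). It adds 0 to about 18 points over a post-value test when 12 mmHg is the SD of one measurement (rho 0 up to 0.7). It would be too strong to say that ANCOVA always gains: steps 5 and 6 show settings with no gain and settings with a loss of about 9 points.

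Confidence is high that no covariate is used and that the planned size reproduces. The size of the benefit in this trial cannot be known from the documents.

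**What to change.** In section 6, 2), before any between-arm outcome data are examined:

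- Make the primary analysis of mean PAP an ANCOVA of the value from the RHC immediately after PEA on arm and the value from the RHC immediately before PEA. Take the adjusted difference, 95% CI and p-value from that one model.
- Pre-specify as sensitivity analyses one named rank-based method (for example Quade's rank ANCOVA with the same covariate) and the planned t-test/Mann-Whitney test, stating whether the latter is on change or on the post-operative value.
- Do not switch the p-value to a rank method on a normality test while the CI stays with ordinary ANCOVA. In simulation with t(3) tails, the two disagreed on significance in about 5-10% of trials.
- Report how many patients per arm have both RHC values.

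**Cost:** a few sentences of SAP text, a little analysis work and one residual degree of freedom (69 instead of 70 with all 72 patients complete). No data are added. A change test needs both RHC values as well, so ANCOVA loses no further patients against it; with 32 complete per arm and rho 0.5 (SD of change 12), power is 75% for change and 86% for ANCOVA.

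**Limits:** if tails prove heavy or skew strong, the primary ANCOVA gives up some power, and the sensitivity analyses will show this but not restore it. Adjustment does not resolve missing post-operative values after peri-operative death, which the plan must handle separately to meet its intention-to-treat commitment.

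### Average cost is a named secondary endpoint, but if cost is skewed the plan's test rule leads to Mann-Whitney, which does not test a difference in means

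*Combined protocol and SAP*

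**What the plan says.** Section 5 (Outcome measures and time frame) ends its list of secondary endpoints with "disease directly associated cost (average cost) in the follow-up period". This is the only mention of cost, and it names the average as the summary.

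Section 6, Statistical Analysis, covers every continuous variable with one sentence: "Significant differences were determined with the Mann-Whitney test or independent t-test according to the their distribution". The criterion for judging the distribution is not given. The default display is also general: "Continuous variables are presented as mean \pm standard deviation, unless otherwise specified". The threshold is common to all tests: "P value less than 0.05 was considered statistically significant". No method is given for cost alone: no interval for a mean difference, no bootstrap and no regression model.

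**The concern.** The two sections answer different questions once cost is skewed. Section 5 asks about average cost. Under Section 6 a skewed variable goes to Mann-Whitney, which asks whether a patient in one arm tends to cost more than a patient in the other, that is, whether P(X > Y) differs from 0.5. By default the table would still show means and standard deviations, so a rank-test p-value would stand beside two means that it does not compare.

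Cost cannot be negative, and a few patients with major complications can be very expensive, so right skew is a reasonable expectation. A lower complication rate in one arm would thin that arm's upper tail, so a difference in shape is possible too. The trial could then report a significant cost difference when average costs are equal, or miss a difference in averages that comes from a few costly patients.

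**Working it through.** **Inputs from the documents.** Endpoint: average cost (Section 5). Test rule, default summary and 0.05 threshold: Section 6. Size: 72 patients in two groups (Section 3), 36 in the precise therapy group (Section 6), from a randomisation list of 50 + 50 (Section 4).

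**The plan's own figure.** Section 6 assumes a difference of 8 mmHg in mean PAP, an SD of 12 mmHg, 80% power and a two-sided 5% level. n per arm = 2 × (1.960 + 0.842)² × 12² / 8² = 2 × 7.85 × 2.25 = 35.3, so 36. The figure reproduces. It concerns mean PAP and does not depend on the cost analysis.

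**Assumption.** The documents give no cost data. Costs are taken as lognormal, with log-SD s1 and s2 in the two arms. The results depend on these values, so a range is shown.

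**Which test the rule selects.** With Shapiro-Wilk at 5% as a stand-in for the unstated criterion, at least one arm was flagged as non-normal in essentially all simulated trials at 36 per arm.

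**Why the two questions differ.** A lognormal mean is exp(μ + s²/2). Equal means require μ1 − μ2 = (s2² − s1²)/2, and then P(X > Y) = Φ[(μ1 − μ2)/√(s1² + s2²)]. For 0.8 vs 1.2:

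- μ1 − μ2 = (1.44 − 0.64)/2 = 0.40
- √(0.64 + 1.44) = 1.442
- P(X > Y) = Φ(0.277) = 0.61

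The means are equal, yet Mann-Whitney's null hypothesis is false. If s1 = s2, then μ1 = μ2 and P(X > Y) = 0.5, and the conflict disappears.

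**Simulated rejection rates, equal true means** (36 per arm, two-sided 5%, 10,000 or 20,000 trials per scenario):

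| log-SD, arm 1 vs arm 2 | Mann-Whitney | Welch t |
|---|---|---|
| same shape | about 5% | about 4% |
| 0.8 vs 0.9 | 6–7% | about 4% |
| 0.8 vs 1.0 | 13% | 5% |
| 0.7 vs 1.0 | 23% | 6% |
| 0.8 vs 1.2 | 36% | 7% |
| 0.5 vs 1.2 (extreme) | 74% | 11.5% |

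More patients do not help. At 0.6 vs 1.0, Mann-Whitney rejects in 35.6% of trials with 36 per arm and in 46.9% with 50 per arm.

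**Unequal means, different shapes.**

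- Equal medians, log-SD 0.6 vs 1.0: the means are exp(0.18) = 1.20 and exp(0.50) = 1.65, a ratio of 1.38. Mann-Whitney rejects in 5.2% of trials, Welch in 15.5%.
- A few costly patients (5% vs 20% of each arm at eight times base cost): the ratio of means is (0.80 + 0.20 × 8)/(0.95 + 0.05 × 8) = 2.40/1.35 = 1.78. Power is 20% for Mann-Whitney and 42% for Welch.
- Log-SD 0.5 vs 1.2, second arm's mean 20% higher: μ1 − μ2 = −0.125 − (−0.72 + ln 1.2) = 0.413, and P(X > Y) = Φ(0.413/1.3) = 0.625. Mann-Whitney ranks the arm with the lower mean as the costlier one, and 45% of trials are significant.

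**Unequal means, same shape.** With a mean 50% higher in one arm, power is 54% for Mann-Whitney and 45% for Welch at log-SD 0.8, and 38% and 27% at log-SD 1.0. Both tests point the same way, and Mann-Whitney is the more powerful.

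**The case against.** A reader might infer that the stated rule gives a wrong result for cost. The documents do not support that. It needs cost to be skewed and its shape to differ between arms, and neither is stated. Both arms receive endarterectomy and differ only in imaging guidance, so similar shapes are quite possible. Mann-Whitney then keeps its level, agrees in direction with the means and has more power. The larger rejection rates also need marked differences in spread: a log-SD of 0.8 vs 1.2 is a coefficient of variation, √(exp(s²) − 1), of about 0.95 vs 1.79. This part of the objection stands and makes the point conditional.

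It can also be said that the word average, in a parenthesis, may name only the summary to be displayed. Section 2 has no economic objective and no cost-effectiveness analysis is planned. That reading is possible. It does not remove the mismatch, because the displayed means would still carry a p-value that does not compare them.

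Lastly, mean-based methods have faults of their own here. Welch rejects in 11.5% of trials in the most extreme equal-mean case, and its power is only 15.5% in the equal-median case. A percentile bootstrap rejects in about 8–11% of trials under equal means when the spreads differ as in the lower rows of the table. This limits the choice of remedy, but in those cases both remain much closer to 5% than Mann-Whitney.

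**Conclusion.** The point holds in conditional form. Section 5 names average cost, and Section 6 would send a skewed cost variable to a test that does not compare averages. That mismatch does not depend on any simulated figure.

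Its practical size does. Under equal means with lognormal costs and 36 per arm, Mann-Whitney's rejection rate runs from about 5% (same shape) through 6–7% (slight difference in spread) to 23% and 36% (marked differences). Welch stays at 4–7% over the same range. The log-SDs are assumptions.

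A reader might also extend this to the main result. Nothing here supports that: the expectation of skewness concerns cost, and the sample size for mean PAP reproduces. Only a secondary endpoint is affected, and the change is desirable rather than essential.

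**What to change.** Add one sentence to Section 6: cost is exempt from the test-by-distribution rule, and the between-group difference in arithmetic mean cost will be reported with a 95% confidence interval whatever the skewness, using Welch's method. Medians and Mann-Whitney may be shown as supportive.

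A bootstrap-t interval is an alternative, but its level at 36 per arm should be checked before it is adopted, because bootstrap intervals for skewed data at this size can also reject too often. A plain percentile bootstrap is not recommended as the main method (about 8–11% rejection under equal means).

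Cost of the change: no new data and no change to the sample size. The interval will be wide for a skewed variable, and power is lower when the arms differ only by a scale factor (about 45% against 54% for a 50% higher mean at log-SD 0.8).

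### WHO functional class is an ordered secondary endpoint, but Section 6 has no rule for ordered categories, and its categorical rule, the most natural fit, ignores the order

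*Combined protocol and SAP*

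**What the plan says.** Section 5 includes among the secondary endpoints "and WHO function classes in the follow-up period". It gives no visit, cut-point or expected difference for this endpoint.

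Section 6, part 2, has three rules for comparing the arms:

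- After a sentence on how continuous variables are presented: "Significant differences were determined with the Mann-Whitney test or independent t-test according to the their distribution".
- For categories: "Categorical variables were compared between the 2 groups using the chi-square test or Fisher exact test".
- For survival: Kaplan-Meier curves with the log-rank test.

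The threshold is common to all of them: "P value less than 0.05 was considered statistically significant". No sentence deals with ordered categories, and none names the test for WHO class. The only power calculation, in Section 6, part 1, concerns mean PAP.

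**The concern.** WHO class runs from I to IV, and the reason to compare it between arms is to learn whether patients function better in one of them. Objective 3 in Section 2 is put in that directional way: it looks for benefits in the precise therapy group.

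The chi-square test and the Fisher test for larger tables respond to any difference in pattern. Relabelling the classes in any order leaves the P value unchanged, so a general move from class III to class II gets no more weight than an equally large but meaningless reshuffle. With four occupied classes, the chi-square test spreads its power over 3 degrees of freedom, whereas a test that uses the order concentrates it on one. In a trial of this size, a real shift in function would more easily be missed.

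**Working it through.** **Inputs from the documents.** Mean PAP difference 8 mmHg ("the mean PAP of patients of PTG can be decreased by 8 mmHg more than that of the traditional group"); SD 12 mmHg ("Given the standard deviation of 12 mmHg was expected in the measurement of mean PAP"); planned power 80% at a two-sided 5% level; stated result: "a sample size of 36 of the PTG group was required". Section 3 plans 72 patients in two groups and Section 4 describes a 50 + 50 randomisation list, so allocation is 1:1 with 36 per arm.

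**Step 1: the plan's own figure.** n per arm = 2 × (1.960 + 0.842)² × 12² / 8² = 2 × 7.85 × 2.25 = 35.3, rounded up to 36. Power at 36: the standard error is 12 × √(2/36) = 2.83, so z = 8/2.83 − 1.96 = 0.87 and power is 80.7%. The stated size is reproduced. It says nothing about power for WHO class.

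**Step 2: analytic check.** A 1-df test with 80% power at two-sided 5% has noncentrality (1.960 + 0.842)² = 7.85. With the same noncentrality, an omnibus chi-square test has 70.9% power on 2 df (three classes) and 64.5% on 3 df (four classes). The losses are 80 − 70.9 = 9.1 and 80 − 64.5 = 15.5 points. Where the 1-df test has 50% power, the 3-df test has 34.5%. Where it has 90%, the 3-df test has 78.4%.

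**Step 3: simulation.** 36 per arm, two-sided 5%, 20,000 trials per scenario. The documents give no class distribution or effect, so **the control splits and odds ratios are assumptions**. The treated arm follows from one common odds ratio (OR) applied to each cumulative probability. For example, with control 40/45/13/2% and OR 2, the odds of class I go from 0.40/0.60 = 0.667 to 1.333, a probability of 57%; the full treated split is 57/35/7/1%.

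Power in %, chi-square / Mann-Whitney with tie correction (loss in points):

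| Control I/II/III/IV, % | OR 1.5 | OR 2 | OR 2.5 | OR 3 | OR 4 |
|---|---|---|---|---|---|
| 40/45/13/2 | 9.0 / 14.4 (5.4) | 20.9 / 32.7 (11.7) | 35.1 / 51.1 (16.0) | 48.5 / 65.2 (16.7) | 69.2 / 83.3 (14.1) |
| 10/30/45/15 | 10.3 / 15.5 (5.2) | 22.5 / 35.6 (13.1) | 37.6 / 54.8 (17.2) | 52.4 / 70.6 (18.3) | 73.6 / 87.7 (14.1) |
| 60/35/4/1 | 8.0 / 13.4 (5.4) | 17.2 / 27.3 (10.0) | 28.9 / 42.3 (13.4) | 39.1 / 54.1 (15.0) | 56.7 / 71.5 (14.8) |
| 50/45/5/0 | 9.8 / 13.9 (4.1) | 22.2 / 29.8 (7.6) | 36.0 / 46.4 (10.4) | 50.0 / 60.8 (10.8) | 68.5 / 78.7 (10.2) |
| 55/45/0/0 | 13.4 / 12.6 (−0.7) | 29.1 / 27.4 (−1.7) | 45.1 / 43.2 (−2.0) | 58.9 / 57.2 (−1.6) | 75.3 / 74.4 (−0.9) |

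(Losses were taken before rounding.) Two further four-class splits, 30/50/15/5 and 20/40/30/10, stay within the same range. With no true difference, the five splits shown give rejection rates of 3.1 to 4.8% for chi-square and 4.6 to 5.1% for Mann-Whitney.

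**Step 4: against Fisher.** With control 30/50/15/5, exact Fisher loses 11, 15 and 12 points at OR 2, 3 and 4; chi-square loses 13, 18 and 15. At OR 2.5 with control 30/50/17/3, the powers of chi-square, Fisher and Mann-Whitney are 35, about 39 and 52%. With control 20/45/30/5 they are 36, about 40 and 53%. The loss against Fisher is therefore about 13 points in both.

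**Step 5: where the ordered test does worse.** If the arms differ without a consistent direction, the advantage reverses. With control 30/50/15/5 against 50/20/20/10, chi-square has 63% power and Mann-Whitney 11%.

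**Step 6: larger enrolment.** If the whole 50 + 50 list were used, the four-class loss would be about 3 to 19 points over OR 1.5 to 5.

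**The case against.** - *The plan never says that WHO class is tested with chi-square or Fisher.* This stands. A reader might infer an explicit assignment, but the text makes none. The Mann-Whitney sentence follows the one on continuous variables without being expressly limited to them. The categorical rule is the likelier reading because classes are categories. If it is not the intended one, the test is unspecified, and the same sentence is needed.
- *No particular power loss belongs to this plan.* This also stands. A flat loss of about 15 points is tempting, since it matches the 3-df calculation and the middle of the four-class results. It needs four occupied classes, a shift in one direction and a moderate to large effect, and the documents state none of these.
- *Fisher is the fairer comparator.* Largely right. In the two OR 2.5 scenarios of Step 4, over 90% of simulated tables have more than 20% of cells with an expected count below 5, the usual trigger for an exact test. The loss is then smaller but does not vanish.
- *A significant chi-square result would still be interpretable.* Partly right. The test has no direction, but the class percentages by arm would show one, so it would be wrong to say that the better arm could not be identified.
- *The ordered test can miss a real difference.* True for patterns such as that in Step 5. Such a pattern would not show that either arm functions better overall, which is the question here.
- *The endpoint is secondary and no power is claimed for it.* True. Even Mann-Whitney reaches only 52 to 53% in the OR 2.5 scenarios of Step 4. This limits the importance of the point, but the change costs almost nothing.

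**Conclusion.** The point holds in conditional form. WHO class is an ordered secondary endpoint, Section 6 has no rule for ordered categories, and its most natural rule discards the order. That much needs no assumption about the data.

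The size does. At 36 per arm, for a one-direction shift with a common odds ratio of 1.5 to 4, chi-square loses about 5 to 18 points against Mann-Whitney with four classes occupied and about 4 to 11 with three. With two there is essentially no loss. Fisher loses somewhat less than chi-square.

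The documents do not support reading this as a fixed loss, as an invalid test (the simulated chi-square error rate stays below 5%), or as a flaw in the primary analysis. The mean PAP comparison and its 36 per arm are untouched. This is an inexpensive improvement to one secondary analysis.

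**What to change.** Add to Section 6, part 2:

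*WHO functional class is compared between arms with the Mann-Whitney test with tie correction; a common odds ratio with 95% CI from a proportional-odds model is reported as the effect estimate.*

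Keep chi-square or Fisher for binary and unordered categorical variables. Restricting them to yes/no outcomes would leave unordered variables with several levels without a test. The model has to be named because Mann-Whitney does not itself give an odds ratio.

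Cost: one SAP sentence and no new data or patients. Mann-Whitney is already in the plan; the proportional-odds model is an addition, and its assumption bears on the estimate only, not on the test. The price is less sensitivity to differences with no consistent direction. The sentence does not settle which of the 3-, 6-, 12- and 24-month visits in Section 3 is used, or how patients who die are classed. Both are best stated alongside it.
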